1.4 Compliance Statement

This study will be conducted in full accordance of all applicable Children's Hospital of Philadelphia Research Policies and Procedures and all applicable Federal and state laws and regulations including 45 CFR 46. All episodes of noncompliance will be documented.

The investigators will perform the study in accordance with this protocol and will report unanticipated problems involving risks to subjects or others in accordance with The Children's Hospital of Philadelphia IRB Policies and Procedures and all federal requirements. Collection, recording, and reporting of data will be accurate and will ensure the privacy, health, and welfare of research subjects during and after the study.

2 STUDY OBJECTIVES

The purpose of the study is to demonstrate acceptance and feasibility of conducting a field trial of cellphone blocking technology between parents and their teen drivers to calculate sample sizes for future trials and generate preliminary data for funding applications. Primarily, the proposed is measuring whether the bidirectional teen-parent monitoring approach decreases overall cellphone use while driving for both teen and parent.

2.1 Primary Objective (or Aim)

The primary objective of this study is to compare measures of acceptance and feasibility of teen-parent dyads randomized to bidirectional teen-parent vs. teen only monitoring of cellphone use while driving in an on-road driving study.

2.2 Secondary Objectives (or Aim)

The secondary objectives are to:

1. To compare the: a) number of cellphone unlocks per hour of drive time; and b) total proportion of non zero-speed drive time spent using a cellphone while driving in teen-parent dyads randomized to bidirectional teen-parent vs. teen only monitoring of cellphone use while driving in an on-road driving study. These estimates will be used to design a future, well-powered study examining the comparative effectiveness of these two approaches as the primary objective.
2. To determine the drive and environmental characteristics of instances in which a phone is unlocked using data collected from the DriveID device overlayed with data collected from Geographic Information Systems (GIS).
3. Measure the reasons cellphones are being used while driving at non-zero speeds among teens and their parents(calls, texts, smartphone apps, etc.)
4. Measure teen and parent satisfaction with the cellphone monitoring and blocking device
5. Determine the incidence of handheld cellphone use while driving and its relationship to incoming text messages and driving conditions in a teen drivers and their parents.
6. Measure the number of phone unlocks per hour of drive time
7. Measure the speed of the car, acceleration, and spatial characteristics of phone unlocks (ex. on highways vs. at intersections)

3 INVESTIGATIONAL PLAN

3.1 General Schema of Study Design

This is a randomized control study of teen only monitoring vs. bidirectional teen-parental monitoring of cellphone use while driving.

3.1.1 Screening Phase

Interested participants can contact a study team member for more information about the study, and/or, they will be directed to the Way to Health platform for more study information as well as consent. All participants who consent will be contacted by a member of the study team to ensure full comprehension of study procedures and requirements.

Participants will also be recruited through posted flyers, postcards, email blasts, through the Recruitment Enhancement Core (REC), social media, and by word-of-mouth/colleague

referrals at Penn and CHOP. The flyers will be posted in a variety of public and private locations, including but not limited to, local public and private high schools in suburban and local Philadelphia, summer camps, universities, etc. No recruitment will occur through schools or public places without first obtaining permission. Postcards will be mailed to potentially eligible families identified by the REC and the Penn Social Media & Health Innovation Lab.

The Penn Social Media & Health Innovation Lab will assist with recruitment through a variety of social media outlets including Facebook and Craigslist. Language for these postings have been included with the application.

Interested participants will be directed to the Way to Health platform. A parent will create an account and consent online. Once consent is obtained, teens will be able to create their own account and assent online. Once consent and assent are obtained, parents and teens will be screened for eligibility with an eligibility survey presented on the Way to Health platform. Only eligibility criteria will be asked. If a participant responds “yes” to all questions, teens and parents will each be presented with an intake survey on the Way to Health platform. Questions will cover demographics, opinions, perceptions and experiences with texting and driving. Both parent and teen will be asked to email the study team a picture of their driver’s license. A member of the study team will also contact the teen to answer any questions and to mail out the CellControl device. If a teen is not eligible, the participant will be informed that they are ineligible for the current study.

If participants turn 18 during the duration of the study, they will be re-consented as an adult through Way to Health.

3.1.2 Baseline Measurement Period (Weeks 1-3)

DriveID will monitor all cellphone use while the participant’s cellphone is in the car in which DriveID is installed. During the Baseline Measurement Period, DriveID will only monitor cellphone use while driving; no blocking will occur. During this period the Cellcontrol app runs in the background.

3.1.3 Intervention Measurement Period (Weeks 4-8)

DriveID will monitor all cellphone use while the participant’s cellphone is in the car in which DriveID is installed. The application will be used as a cellphone blocking device where the phone will lock the phone screen while driving and block incoming calls and texts. The locking function can be overridden with a tap of a button on the home screen. This use of this application has been approved by IRB proposal 14-11234 for use in a teen driver cohort. DriveID continuously monitors cellphone use while driving, regardless of whether the blocking function is activated, including how often the teen and/or parent unlocks the cellphone as well as if they are using the phone for a call or other handheld phone features. However, DriveID is not able to differentiate which phone features are being used. DriveID will capture GPS data throughout the measurement period. A survey following the baseline period (end of Week 3) will be administered to gain feedback. At the completion of Week 8 or upon voluntary withdrawal from the trial, the participants will be instructed to complete an online survey administered through Penn’s Way to Health IT

platform asking about user satisfaction with the device and its configurations. Participants will also be asked to complete a semi-structured phone interview after study completion.

The study team does not promote texting and driving and encourages all participants to drive safely.

3.2 Allocation to Treatment Groups and Blinding

Participants will be randomized to one of two groups. The randomization chart will be maintained will be maintained on a secure server that is only accessible by key study personnel.. Participants and study staff will be aware of which group they have been assigned to.

3.3 Study Duration, Enrollment and Number of Sites

3.3.1 Duration of Study Participation

The study duration per subject pair will be up to eight weeks.

3.3.2 Total Number of Study Sites/Total Number of Subjects Projected

The study is being conducted at the Children's Hospital of Philadelphia and the University of Pennsylvania. It is expected that a maximum of 250 people will participate in this research study.

3.4 Study Population

3.4.1 Inclusion Criteria

Teen:

- 1) Is a high school student (age 16 or 17 at start of the study)
- 2) Holds a valid driver's license
- 3) Lives in parent/guardian's home
- 4) Primarily drives one car
- 5) Drives an average of 4 or more trips per week
- 6) Has their own iPhone 4S or newer or Android 4.3 or newer smartphone with data plan
- 7) Admits to texting while driving at least once in the last month

Parent:

- 1) Is the parent of a teen driver
- 2) Drives an average of 4 or more trips per week
- 3) Primarily drives one car
- 4) Has their own iPhone 4S or newer or Android 4.3 or newer smartphone with data plan

5) Admits to texting while driving at least once in the last month

Both parent and teen will be enrolled together as a pair.

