1.2 Name and Description of Intervention

Cellcontrol DriveID was released in December of 2013 as a device to overcome a technological barrier in being able to accurately measure whether a driver's cellphone is being used while driving. It is a solar-powered Bluetooth signaling technology placed on the car windshield. DriveID can measure type of cellphone use while driving and be configured to block a driver's cellphone use while the vehicle is in motion. There is no physical interaction with the DriveID device other than installation.

The device is placed on the windshield and an app is downloaded on to the phone. Online configuration of the device settings takes approximately 3-5 minutes. After the initial installation, the device is always on and interacts with the user's cellphone in the background. Only the cellphone with the corresponding DriveID application is monitored by the DriveID device. The DriveID device directly measures the vehicle's movements and can be set to lock the phone at speeds as low as 1 mph. Device setup is flexible to allow specific smartphone applications like navigation and maps to be used if initiated when stopped. The blocking function cannot be deactivated without permission of the account holder.

The study intervention involves randomization into one of two conditions: teen-parent monitoring and teen only monitoring. In the bidirectional teen-parent monitoring condition, the teen driver will receive an automatic notification (via email) when one of his or her parents overrides the DriveID blocking function to use their phone while driving along with the parent receiving a notification when their teen overrides the blocking function. The teen only monitoring condition only involves the parent/guardian receiving a notification (via email) if their teen overrides the DriveID blocking function. Furthermore, if anyone tampers with the DriveID device, delete the corresponding application from their smartphone, or disable Bluetooth capabilities, an email will be sent to a member of the study team.

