Forty-four participants each received a cell phone filtering/blocking application on their employer-provided cell phones for 9 weeks. During the first and last 3 weeks, cell phone activity including calling, text messaging and application use was simply recorded in the background. During the middle 3 weeks, the cell phone filtering/blocking software was active, meaning that anytime the application sensed that the phone was moving faster than the pre-set speed threshold, all phone activity was blocked. Objective data on participants' phone use behavior and subjective data (from a questionnaire) on participants' acceptance were collected. Additionally, the impact on an organization attempting to implement a similar program employing cell phone filtering/blocking was examined. During the blocking period, participants initiated a higher proportion of their calls when stopped than when the blocking software was inactive. Also, during the blocking period, participants answered a much smaller proportion of incoming calls while driving, and outgoing calls were placed at a lower mean speed. Participants were neutral in their opinions on whether they received a safety benefit from the cell phone blocking.

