3.4.2 Exclusion Criteria

- 1) Parent and/or teen already uses a smartphone app or hardware device to limit cellphone use while driving

Subjects that do not meet all of the enrollment criteria may not be enrolled. Any violations of these criteria must be reported in accordance with IRB Policies and Procedures.

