6.1 Primary Endpoint

In determining feasibility the following endpoints will be measured:

- Proportion of screen eligible who enroll
- Number enrolled per month
- Retention rates by study arm
- Proportion of surveys completed
- Acceptance of cellphone blocking strategy measured on Likert scale in post-study survey

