6.4.1 Teen-Parent Monitoring Group

The blocking settings will turn on by default while driving. Blocking settings will be pre-set to block all incoming calls and text messages while the vehicle is in motion, but participants will have the ability to override the blocking. Number of unlocks can be monitored through logging in to the Cellcontrol website.

In the bidirectional monitoring arm, the teen will receive an email notification when their parent unlocks their phone while driving and vice versa.

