6.4.2 Teen Only Monitoring Group

The blocking settings will turn on by default while driving for both the teen and parent. Blocking settings will be pre-set to block all incoming calls and text messages while the vehicle is in motion, but participants will have the ability to override the blocking. Number of unlocks can be monitored through logging in to the Cellcontrol website.

The teen only monitoring group involves parental monitoring of teen's cellphone use while driving only. The parent will receive an email notification when their teen unlocks their phone while driving. Both parent and teen will drive under the same restrictions, but only the parent will be notified of teen cellphone use.

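### DriveID records only the registered phone, so parents in the bidirectional arm could move use to another phone and lower measured parent use without a real change

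*Combined protocol and SAP*

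**What the plan says.** The combined protocol and SAP sets the same phone criterion for teen and parent in section 3.4.1: "Has their own iPhone 4S or newer or Android 4.3 or newer smartphone with data plan". The single exclusion in section 3.4.2 is "Parent and/or teen already uses a smartphone app or hardware device to limit cellphone use while driving". Neither mentions a second phone.

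Section 1.2 limits what is measured: "Only the cellphone with the corresponding DriveID application is monitored by the DriveID device". It does anticipate evasion. If anyone tampers with the device, or should they "delete the corresponding application from their smartphone, or disable Bluetooth capabilities, an email will be sent to a member of the study team".

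Blocking runs for parent and teen in both arms, and teen unlocks go to the parent in both. The arms differ in what happens to the parent's unlocks. In the bidirectional arm (section 6.4.1), "the teen will receive an email notification when their parent unlocks their phone while driving and vice versa". In the teen-only arm (section 6.4.2), "Both parent and teen will drive under the same restrictions, but only the parent will be notified of teen cellphone use".

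The primary endpoints in section 6.1 are enrolment, retention, survey completion and acceptance. Phone use is secondary (section 6.2) and is to be summarised descriptively by arm, with a multilevel model described as likely (section 6.3.2). Section 2.2, objective 1, says these estimates will be used to design a later, adequately powered trial. Section 2 also states the study's main interest as whether bidirectional monitoring lowers phone use in both teen and parent.

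**The concern.** A call or text on an unregistered phone during a recorded trip is not blocked, not logged and not reported to anyone. It sets off none of the section 1.2 alerts, because the device, the app and Bluetooth on the registered phone all keep working. In the data, a parent who stops using the phone and a parent who changes phones look the same: drive time accrues while recorded unlocks and time in use fall.

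If this happened equally in both arms it would cancel in the comparison of relative use. It need not be equal, since only bidirectional-arm parents have their unlocks emailed to their teen. Measurement error that depends on the assigned arm is not removed by randomisation. The baseline weeks do not remove it either, because blocking and notification begin only with the intervention period, so any displacement would appear as within-person change after assignment. An overstated difference carried into the next trial's planning would make that trial too small.

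**Working it through.** The documents give no effect size, standard deviation, power calculation or rate of second-phone use, so there is no figure of theirs to reproduce. The check has two parts.

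**Would anything planned detect it?**

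- Eligibility (3.4.1, 3.4.2): asks for one suitable phone and excludes existing blocking tools. Another phone is not covered.
- Alerts (1.2): device tampering, app deletion, Bluetooth off. A second phone triggers none of them.
- Intake survey topics (5.2): the parent list includes use of wireless technology while driving, which is not confined to the registered phone, but it is collected before assignment.
- End-of-baseline survey topics (5.4): self-reported phone use, for the three baseline weeks only.
- End-of-study survey topics (5.5): feedback, settings, perceived safety and suggestions. Self-reported phone use and other phones are not listed.

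For the intervention weeks, then, no listed data would show displacement.

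**How large could it be?** All three inputs are assumptions:

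- f = share of parents with a second phone they would use while driving
- s = share of their in-drive use that they move to it in the bidirectional arm
- r = shift in the teen-only arm as a fraction of that in the bidirectional arm

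True use is taken as equal in both arms, and parents with a second phone are taken to use phones about as much as other parents.

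Apparent reduction in parent use = 1 − (1 − f·s)/(1 − r·f·s).

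If parent and teen each contribute half of the dyad's use, the dyad-level reduction = 1 − [0.5 + 0.5(1 − f·s)]/[0.5 + 0.5(1 − r·f·s)].

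With f = 20% and s = 50%, f·s = 0.10:

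- r = 0: parent 1 − 0.90/1 = 10%; dyad 1 − 0.95/1 = 5%.
- r = 0.5: parent 1 − 0.90/0.95 = 5.3%; dyad 1 − 0.95/0.975 = 2.6%.
- r = 1: both 0%.

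| f | s | Parent, r = 0 | Parent, r = 0.5 | Dyad, r = 0 | Dyad, r = 0.5 |
|---|---|---|---|---|---|
| 5% | 25% | 1.25% | 0.6% | 0.6% | 0.3% |
| 10% | 50% | 5.0% | 2.6% | 2.5% | 1.3% |
| 20% | 50% | 10.0% | 5.3% | 5.0% | 2.6% |
| 30% | 100% | 30.0% | 17.6% | 15.0% | 8.1% |

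Every row is 0% at r = 1, and so is any row with f = 0. The last row is an extreme in which all use is moved.

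**The case against.** The strongest reply is that this is a possibility and not a demonstrated bias. It needs parents who have a second phone and who move more use to it in one arm than in the other, and the documents support neither with a figure. A reader might take the employer-provided phones in the earlier field study (section 1.3) as evidence that second phones are common. They are not: participants there received a "cell phone filtering/blocking application on their employer-provided cell phones for 9 weeks", so those were the monitored phones, and the text says nothing of others. That part of the objection stands.

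It also stands that blocking gives parents in both arms some reason to switch, that an override takes one tap, and that the only arm-specific consequence described for the parent is an email to the teen. Payments in section 8.7.1 are for surveys and interviews and do not depend on unlocks. The extra motive may be weak. For teens, notification is the same in both arms, so this argument gives no differential motive.

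The questionnaires themselves are not in the documents, only topic lists, so a suitable item may already exist. Finally, the gap comes from what DriveID can measure more than from the eligibility wording. A sole-phone criterion would rest on self-report before randomisation, could not prevent later use of another phone, and would narrow a feasibility sample.

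What the objection does not remove is that recorded parent use cannot separate real reduction from displacement, and that nothing listed for the intervention weeks would help to do so.

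**Conclusion.** The point holds as a possible bias of unknown size in measured parent phone use, in favour of the bidirectional arm. With 20% of parents having a second phone and half their use moved, it runs from 0% (equal shifting) through about 5% (half as much shifting in the teen-only arm) to 10% (shifting in the bidirectional arm only). At dyad level it is about half that if parent and teen contribute equally. These are illustrations under assumed values, and the documents cannot say which applies.

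Two stronger readings are tempting and not supported. One is that the bidirectional arm will look better with no change in behaviour; that requires unequal shifting, which is plausible but not shown. The other is that the trial's main results are compromised. Section 6.1 introduces its list with "In determining feasibility the following endpoints will be measured", and none of the items there depends on DriveID usage data. What is at stake is the secondary parent comparison and its use in planning the next trial.

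**What to change.** At intake, ask each participant whether they use any other phone while driving, and install the app on it where the system allows. This parallels the rule in sections 4.2 and 8.7.2 that the cars driven by the dyad receive a device. The documents do not say whether one person can register several phones, so confirm that with the vendor.

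Add one item to the end-of-baseline and end-of-study surveys on use of any other phone while driving in that period. Tabulate it by arm and by parent or teen, and read the parent phone-use comparison in that light, for example with a sensitivity summary that leaves out parents reporting such use. The end-of-study answer comes after assignment and may itself depend on arm, so leaving parents out on that basis is a sensitivity check only. Grouping by the intake answer, given before assignment, keeps the randomised comparison intact.

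Do not add a sole-phone exclusion criterion.

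The cost is one or two extra questions in surveys already given and an extra app installation for a few participants. The remaining weakness is reliance on self-report. The answers cannot be collected contemporaneously once the trial has ended.

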3.4.2 Exclusion Criteria

- 1) Parent and/or teen already uses a smartphone app or hardware device to limit cellphone use while driving

Subjects that do not meet all of the enrollment criteria may not be enrolled. Any violations of these criteria must be reported in accordance with IRB Policies and Procedures.

4 STUDY PROCEDURES

4.1 Screening Procedure and Online Consent/Assent Process

Potential participants will be recruited through methods discussed in section 8.5. Teens and parents will be instructed that the parent first needs to create an account through the WTH platform and then review a consent and sign prior to their teen being screened for the trial. Way to Health collects basic demographic information from every person creating an account, including date of birth. After a parent consents for them and their teen to participate, parents will be presented with an eligibility survey. If eligible, they will be instructed to have their teen go to the WTH site and register. Teens will then review and sign an assent for the trial. Following this they will be screened with an eligibility survey presented on the WTH platform. If a participant is eligible, they will be allowed to continue in the trial and will be asked to complete the intake survey immediately. Questions will cover demographics, opinions, perceptions and experiences with texting and driving. They will then continue on with their trial participation. If they are not eligible, the participant will be informed that they are ineligible for the current study and will not complete any study procedures. These teens will be documented as screen failures. After teen assent and eligibility is completed, parents will be able to sign back into Way to Health and complete the intake survey.

Teens and parents will be asked to email the study team a copy of their driver's license. A member of the study team will then contact the teen and parent/guardian to schedule an in person meeting or a phone meeting. During this meeting the study team will answer any questions pertaining to the consent or the study and distribute the DriveID device in person or by mail. If a participant turns 18 years old during their participation in the study, a member of the study team will email the teen a link to complete the online consent via WTH in order to re-consent. Participants will receive an email or a text message reminder regarding incomplete steps in WTH depending on their preference selection for communication.

The validation of the online consent/assent process will be met during this meeting and allow for the fulfillment of one of the study aims: to demonstrate the feasibility and effectiveness of an online consent process in order to remotely recruit a larger number of participants in future studies among those who purchase the Cellcontrol product. During the meeting, a member of the study team will ensure that the participants truly understand the

risks and benefits of the study. If any participants wish to withdraw, they may do so at this time.

